6 STUDY SETTING

This will be a single-center (Addenbrooke's Hospital) prospective study utilising a new treatment algorithm using lactate/pyruvate ratio to direct management following traumatic brain injury. We will assess patients admitted to the neuro-critical care unit to see if they are eligible for inclusion.

7 SAMPLE AND RECRUITMENT

7.1 Eligibility Criteria

We will include patients with traumatic brain injury in need of intracranial monitoring admitted to the in the neuro-critical care unit, fulfilling the inclusion criteria.

7.1.1 Inclusion criteria

a) Patients with head injury requiring ICP monitoring

b) Age 18-65 years

Directed management in brain injury.

c) Abnormal CT scan

7.1.2 Exclusion criteria

- a) Bilateral fixed and dilated pupils
- b) Bleeding diathesis
- c) Thrombocytopenia (platelets < 100)
- d) Devastating injuries; patient not expected to survive > 24 hours
- e) Brainstem damage
- f) Pregnancy
- g) Involvement in other studies non-observational studies
- h) MD catheter located in haemorrhagic lesion

7.2 Sampling

All patients will have a full medical history taken and a clinical examination. The following are to be recorded:

- a) Weight and BMI
- b) Sex
- c) Age and date of birth
- d) Any significant past medical history
- e) Full blood count (including platelets and differential white cell count)
- f) Biochemical series (including urea, creatinine, uric acid, electrolytes, calcium, alkaline phosphatase, AST, CRP and serum glucose)
- g) Initial Glasgow Coma Scale score
- h) Focal neurological deficit
- h) CT diagnosis, Marshall and Rotterdam score
- i) Drug dosages of paralyzing and sedating agents
- j) Drug doses of vasoactive agents
- k) Fraction of inspired oxygen (FiO₂), partial pressure of oxygen in arterial bloods (PaO₂) partial pressure of carbon-dioxide in arterial blood (PaCO₂)

Study Assessments

Dynamic	Multi-modality monitoring (ICP, CPP, PbtO ₂), MAP, FiO ₂
Every 30 minutes	Microdialysis Parameters
Hourly	GCS, Clinical examination, PaO ₂ , PaCO ₂ , serum sodium, serum glucose
2xDaily	Serum and if possible CSF sampling.

Brain imaging will be performed when clinically indicated.

All monitored parameters will be extracted automatically and stored on hospital computers as part of conventional care. Microdialysis sampling, as part of the standard routine, will be done twice hourly where 20 µl will be extracted. If the patient has an extra-ventricular drain, it will be used to sample cerebrospinal fluid as part of standard routine in the department (200 µl per sample, if available). Blood samples will be drawn twice daily, and we will use discarded samples for analysis (200µlx2 per day).

Directed management in brain injury.

7.2.1 Size of sample

The aim is to reach a sample size where there is a statistical difference between patients with different pathological targets. It is difficult to assess what this sample size is considering this has never been done before, but we estimate that a n=100 will suffice.

7.2.2 Sampling technique

All monitored samples will be digitally stored automatically. All bodily fluids will be sampled at convenience, as these samples would have been otherwise discarded.

7.3 Recruitment

Members of the research team will daily approach the staff in the neuro-critical care unit to determine if any of the newly admitted patients are eligible for inclusion in the study.

7.3.1 Sample identification

Members of the research team, together with the staff in the NCCU at Addenbrooke's Hospital, will identify patients eligible for inclusion.

7.2.2 Consent

The next-of-kin, or consultee, will be informed about the study and will have to provide written assent as patients who require multimodality monitoring are unconscious and not able to give consent. Patients will, after regaining consciousness, be given the option to consent into the study, or withdraw if they choose, without prejudice for future care.

8 ETHICAL AND REGULATORY CONSIDERATIONS

The main ethical issue is that the eligible patients will be unconscious at admission to the hospital and the neuro-critical care unit and therefore not be able to provide an informed consent. In these cases, family and next of kin will be asked if they will allow the patient to take part in the study. The study will not specifically withhold treatments from any patient, we will be delivering treatments that would be considered anyway, but in a structured fashion.

Data collection and storage will be done in password protected computers, and blood/CSF samples will be stored in locked freezers, at the University of Cambridge.

The protocol is in line with relevant legislation and regulation.

Directed management in brain injury.

8.1 Assessment and management of risk

The study is designed to closely follow the standard clinical management of traumatic brain injury. Patients with injuries severe enough to participate in this study are by definition unconscious, and will not suffer any discomfort from the study. We will work closely with the treating clinicians and ensure that they are happy with every aspect of the protocol in each individual patient and that the opinion of the treating clinician is respected.

As this protocol is a more structured version of the conventional therapy provided on a regular basis, we do not believe that there will be any additional risks with this protocol.

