3 THEORETICAL FRAMEWORK

We aim to include all traumatic brain injured patients admitted to the neuro-critical care unit that are being monitored and have multi-modality monitoring already in place. As all patients will follow the same protocol, we will minimize the risk of selection and researcher bias. As the patient will be unconscious during this process, next of kin will be asked for consent. As mentioned, this is a structured form of the standard treatments already provided in intensive care.

We will specifically identify patients in whom the microdialysis lactate:pyruvate ratio (LPR) increase above 25. This threshold has been proven to relate to a worse outcome after head injury. This will trigger our protocol which will consist of the following steps:

1. If ICP >20 mmHg, we will aim to escalate intracranial pressure decreasing measures by administering hypertonic saline (5%) 100 ml and if necessary continue on with further ICP decreasing measures.
2. If the brain oxygen pressure falls <15 mmHg, and the pressure reactivity index is >0.3 (an indication that the normal auto-regulation of the brain blood flow is not functioning properly), will increase the cerebral perfusion pressure by 10-20 mmHg.
3. If this still does not improve the brain oxygen pressure, we will increase the flow of inspired oxygen up to a maximum of 60-80%.
4. These steps do not adjust the LPR and if there is a decrease in glucose in the affected brain tissue (<1 mmol/l), we will increase the plasma glucose levels to a maximum 10 mmol/l in order to ensure that the correct amount of nutrients is being delivered, using 50% dextrose (sugar) solution.
5. If all the above steps fail to improve the LPR, it could be due to mitochondrial failure, the powerhouse of the cell. There are currently no approved therapies for this condition. However, at the treating physicians discretion, energy supplementation (e.g. succinate) or neuro-protective drugs (e.g. cyclosporine A) could be provided.

Directed management in brain injury.

Following a 6 month period, we will see the patients in our outpatient clinic to assess functional outcome. This is part of the patient's standard clinical care as all our patients are offered clinical follow up in this way.

We will collect any biological samples that are available as part of the standard clinical care of the patient and will not subject the patients to any additional procedures. This would consist of:

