4.1 Objectives

1. We wish to determine which of the provided therapies that was superior to others in improving the deranged brain metabolism.
2. We also wish to determine the inter-relationships between parameters detected using the microdialysis and other monitoring techniques, such as brain oxygen saturation and perfusion pressure in the damaged brain, and how microdialysis may complement these techniques.
3. How the protocol will alter cytokine, chemokine and markers of brain damage markers (S100B) in serum and microdialysate for patients suffering from different pathological states?
4. How will the functional outcome distribution be for patients suffering from different pathological states?

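### The reason Section 8.1 gives for expecting no additional risks does not cover step 5 of the algorithm, and the visible text sets up no formal adverse-event recording

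*Protocol*

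**What the plan says.** Section 8.1 states its conclusion and its one reason in a single sentence. The reason is "As this protocol is a more structured version of the conventional therapy provided on a regular basis" and the conclusion is "we do not believe that there will be any additional risks with this protocol". The same premise appears twice more. Section 3 says "this is a structured form of the standard treatments already provided in intensive care", and Section 8 says "we will be delivering treatments that would be considered anyway, but in a structured fashion".

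Section 3 also lists the five steps that a lactate:pyruvate ratio (LPR) above 25 sets off. The first four are pressure-lowering measures, raised perfusion pressure, more inspired oxygen, and glucose. Step 5 begins "If all the above steps fail to improve the LPR" and puts the failure down to possible mitochondrial dysfunction. It adds "There are currently no approved therapies for this condition" and continues that, if the treating physician so chooses, "energy supplementation (e.g. succinate) or neuro-protective drugs (e.g. cyclosporine A) could be provided".

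On safety, Section 8.5 makes a general commitment to safe conduct and GCP, with sponsor monitoring or audit. Section 8.6 deals with protocol deviations, and Section 8.2 with annual reports to the ethics committee. Section 4.2 names an LPR outcome only.

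**The concern.** A risk statement that rests on one premise is only as wide as that premise. If the algorithm merely orders treatments already in regular use, it is reasonable to expect no added risk. Step 5 is different on its face: the protocol itself says that nothing is approved for the condition being treated, and then names candidate agents.

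The patients are unconscious and enter on the written assent of next of kin or a consultee, so the risk section carries more weight than usual. If an agent in step 5 did cause harm, the visible plan has no field in which that harm would be entered as an adverse event, and none that would link it to the agent. The study would then end without adverse-event data on the least established part of its own algorithm.

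**Working it through.** No arithmetic applies, and the plan has no figure here to reproduce. The check sets the texts side by side.

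1. **Is step 5 part of this protocol?** Yes. Section 3 lists it as the last of the five steps set off by a raised LPR. Exclusion criterion (g) in Section 7.1.2 keeps out patients who are in other non-observational studies. The safety procedures of a separate interventional trial would therefore not be expected to cover these agents.

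2. **Does the premise reach step 5?** Section 8.1 relies on therapy given regularly, Section 3 on standard treatments, and Section 8 on treatments that clinicians would have considered in any case. Step 5 says that no therapy is approved for the condition. Nothing in the protocol says that succinate or cyclosporine A is in regular use in this unit for this purpose. Both are given only as examples, so the class is open, and no dose or agent-specific safeguard is stated. The premise is never connected to this step. One step of five is left without the support that Section 8.1 claims for the whole.

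3. **Is there another reason that would carry the conclusion?** Section 8.1 also says that patients are unconscious and will feel no discomfort, and that the treating clinician's view is respected. The first point concerns discomfort, not harm. The second limits when the step is used, but does not describe its risk.

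4. **What would show harm?**
 - Section 7.2 provides continuous intracranial, perfusion and arterial pressure and brain oxygen; hourly coma score, clinical examination, blood gases, sodium and glucose; and serum sampling twice a day.
 - Section 5 provides S100B, the extended Glasgow Outcome Score and SF-36, with the two questionnaires used at the six-month follow-up.
 - These would show neurological and physiological decline, and the outcome scale would probably show deaths.

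5. **What would record harm as an adverse event?** Nothing in the visible text of Sections 4.2, 5, 7.2, 8.1, 8.2, 8.5, 8.6 or Appendix 2 defines adverse events or says how they are recorded or reported.

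6. **Would the exposure be recorded?** Possibly. Therapy intensity levels in Section 5 and treatment observation in Appendix 2 may pick it up. Section 7.2 names doses of sedating, paralysing and vasoactive drugs, but not the agent, dose or start time for step 5. Timing an event against a step-5 dose is therefore not assured.

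**The case against.** The strongest reply is that lack of approval for a condition is not the same as lying outside a unit's practice. Section 8 says that the treatments would have been considered anyway. Step 5 is optional, comes last and depends on the treating physician. All of that stands, and it limits the point: the documents do not show that these agents are foreign to the unit, or that step 5 adds risk. It does not supply the missing link between the premise and step 5.

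Four stronger readings are tempting, and the documents do not support them.

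- *A reader might infer that harm could not be detected at all.* Sections 5 and 7.2 contradict that. What is missing is formal adverse-event recording and a link to the agent.
- *A reader might infer that deaths go uncaptured.* The six-month outcome scale would probably capture them, though without timing relative to a dose.
- *A reader might infer that the ethics committee was not told of step 5.* Section 8.2 sends it all protocols, so step 5 is before it. The patient and consultee information sheets listed in Appendix 1 are not available here and may describe the risk. Only the reasoning in Section 8.1 is open to criticism.
- *A reader might infer that an LPR below 25 reached after step 5 will be credited to the earlier steps.* No section says so. Objective 1 asks "which of the provided therapies that was superior to others in improving the deranged brain metabolism", and Section 4.2 speaks of different treatment strategies. How results are tabulated is commonly left to an analysis plan.

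The GCP commitment in Section 8.5 is relevant but general, and it sets no recording procedure. Adverse-event recording belongs in a protocol, so an analysis plan that is not shown would not be expected to fill the gap.

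**Conclusion.** The point holds in a limited form. The reason Section 8.1 gives for expecting no additional risks does not cover step 5, and no visible section sets up formal adverse-event recording. Followed as written, the plan would yield no adverse-event data as such for the step-5 agents.

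The size cannot be computed. The protocol plans 100 patients but gives no rate of reaching step 5, so the number exposed could be anywhere from 0 to 100. It also gives no dose, no event rate and no comparator. What can be stated is the scope: one of the five steps.

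Two assumptions remain. Some pages were removed from the copy reviewed, so the absence of adverse-event recording is asserted for the visible text only. It is also assumed that no separate document, such as a sponsor procedure, sets adverse-event recording for this study. The point should be corrected before enrolment, because the correction is cheap and the patients cannot consent for themselves.

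**What to change.** Before enrolment, do one of the following.

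- Remove step 5 from Section 3.
- Keep it, and replace the sentence in Section 8.1 with one saying that step 5 uses agents not approved for this condition and may carry added risk. Bring the matching statements in Sections 3 and 8 into line.

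If step 5 stays, add fields for the agent, dose and start time. Record adverse events during protocol-directed treatment, at minimum from the first step-5 dose. Use laboratory tests already collected under Section 7.2, such as creatinine, AST and the full blood count, repeated as clinically available because that section sets no repeat schedule for them.

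The cost is a wording amendment to three sections and a few extra fields. At the minimum scope, those fields apply only to patients who receive a step-5 agent. Recording adverse events throughout protocol-directed treatment would add some work for every patient.

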8.2 Research Ethics Committee (REC) review & reports

Before the start of the study, approval will be sought from REC and IRAS, this include all protocols, informed consent forms and other relevant documents.

All correspondence with the REC will be retained.

The chief investigator will produce annual reports as required and will notify the REC at the end of the study.

8.3 Peer review

The protocol has been reviewed extensively within the research team and with staff from the neuro-critical care unit during several meetings and has been approved by the head the unit.

The protocol was discussed at the International Consensus Meeting on Microdialysis 2014 (external peer review). The results of this meeting are published as a scientific paper and outline the scientific rationale for the study.

8.4 Patient & Public Involvement

We have a longstanding interest in traumatic brain injury research and patients. As well as dealing with patients and their families in their acute stay, we have a multi-disciplinary neurotrauma clinic that combines healthcare professionals from neurosurgery, neurorehabilitation, neuropsychology as well as the Headway Brain Injury Charity.

The details of a project such as this require specialist knowledge to fully appreciate the clinical need and scientific design of the study, however, our commitment to head injury extends to improving every aspect of patient care as demonstrated by our long track record in this field.

8.5 Regulatory Compliance

Before patients will be enrolled in the current study, necessary regulatory measures will be taken through NHS R&D (the Sponsor). We will work in partnership with the study sponsor to ensure the study is conducted in a safe fashion and complies with all aspects of GCP. The sponsor has arrangements in place to monitor or audit the conduct of this study as part of the sponsor's obligations under the Department of Health's Research Governance Framework.

For any amendment that will potentially affect a site's NHS permission, the Principal Investigator or designee will confirm with that site's R&D department that NHS permission is ongoing

Directed management in brain injury.

8.6 Protocol compliance

Any accidental protocol deviation will be adequately documented on the relevant forms and reported to the Chief Investigator and Sponsor immediately. Deviations from the protocol which are found to frequently recur are not acceptable, will require immediate action and could potentially be classified as a serious breach.

8.7 Data protection and patient confidentiality

The Principal Investigator will be responsible for access to any source data. Only defined researchers will be delegated this responsibility.

It is expected that the data generated from the study will be kept on electronic media in the form of a database. This will be kept on computers which are password protected and under the care of the research team. Data from the study will be kept on digital media for a period of ten years to assist in the design and implementation of future studies.

Any stored tissue (blood and CSF) samples will be kept anonymized in a locked freezer.

8.8 Indemnity

As NHS will act as a sponsor, the standard NHS indemnity scheme will apply.

8.9 Amendments

Currently no amendments to the protocol

8.10 Access to the final study dataset

Only members of the study team will have access to the final dataset.

9 DISSEMINATION POLICY

9.1 Dissemination policy

The authors will own the data following completion of the study. Upon completion of the study, the data will be analysed and tabulated and a Final Study Report prepared accessible via the University of Cambridge website. We aim to publish the study in an open-access peer-reviewed scientific journal, where the public will be able to access it. While the funding bodies will be acknowledged, they have no role in the assessment of data or preparation of the study.

The study participants will be informed by the results of the study, as mentioned in the Patient Information Sheet.

11. APPENDICIES

11.1 Appendix 1- Required documentation

- Short CV from Principal Investigator
- Patient consent form Version 1.0, Date 31/10/2016
- Patent information sheet Version 1.0, Date 31/10/2016
- Consultee declaration form Version 1.0, Date 31/10/2016
- Consultee information sheet Version 1.0, Date 31/10/2016

11.2 Appendix 2 – Schedule of Procedures

Procedures	Visits (insert visit numbers as appropriate)				
	Screening	Baseline	Week 1-2	6 Months	
Informed consent	x				
Demographics		x			
Medical history		x			
Observation of treatment		x	x		
Monitoring			x		
Follow-up interview				x	

13.3 Appendix 3 – Amendment History

Amendment No.	Protocol version no.	Date issued	Author(s) of changes	Details of changes made

Currently no existing amendments.
